**Dose modification and toxicity management guidelines for immune-related AEs associated with nivolumab**

Immune-related AEs	Toxicity grade or conditions (CTCAEv4.0)	Management	Monitor and follow-up
Diarrhea / Colitis	Grade 1 (<4 stools per day over baseline; asymptomatic colitis)	Continue per protocol Symptomatic treatment	Close monitoring for worsening symptoms Educate patient to report worsening immediately If worsens, treat as grade 2 or 3/4
	Grade 2 (4-6 stools per day over baseline; IV fluids required < 24 hours; not interfering with ADL. Colitis:)	Delay nivolumab per protocol Symptomatic treatment	If improves to grade 1, resume nivolumab per protocol  If persists > 5-7 days or recurs: 0.5-1.0 mg/kg/day methylprednisolone or oral equivalent

	abdominal pain, blood in stool		When resolves to grade 1, taper steroids over at least one month, consider prophylactic antibiotics, and resume nivolumab  If worsens or persists >3-5 days with oral steroids, treat as grade 3/4
	Grade 3-4 ( $\geq 7$ stools per day over baseline; IV fluids $\geq 24$ hours; interfering with ADL. Colitis: severe abdominal pain, medical intervention required, peritoneal signs. Grade 4: life threatening, or perforation	Discontinue nivolumab  1.0 to 2.0 mg/kg/day methylprednisolone or IV other corticosteroid equivalent  Add prophylactic antibiotics for opportunistic infections  Consider lower endoscopy	If improves, continue steroids to grade 1, then taper over at least one month  If persists > 3-5 days, or recurs after improvement: Add infliximab 5 mg/kg (if no contraindication). Note: infliximab should not be used if perforation or sepsis
Renal	Grade 1 (creatinine $>$ ULN and $>$ baseline, but $\leq 1.5 \times$ baseline)	Continue as per protocol  Monitor creatinine weekly	If returns to baseline, monitor creatinine as per protocol  If worsens, treat as grade 2 or 3/4
	Grade 2-3 (creatinine $>1.5 \times$ baseline and $\leq 6 \times$ ULN)	Delay nivolumab  Monitor creatinine daily  0.5 to 1.0 mg/kg/day methylprednisolone or oral equivalent  Consider bx or renal consult	If returns to grade 1: Taper steroids over at least 1 month, consider prophylactic antibiotics, resume nivolumab and creatinine monitoring as per protocol  If elevation persists > 7 days: Treat as grade 4
	Grade 4 (creatinine $> 6 \times$ ULN)	Discontinue nivolumab  Monitor creatinine daily  1.0 to 2.0 mg/kg/day methylprednisolone or IV other corticosteroid equivalent  Consult nephrologist, consider biopsy	If returns to grade 1: Taper steroids over at least 1 month, and add prophylactic antibiotics for opportunistic infections
Pneumonitis	Grade 1 (radiographic changes only)	Consider delay of nivolumab  Monitor symptoms every 2-3 days  Consider pulmonary and ID consults	Reimage at least every 3 weeks  If worsens, treat as grade 2 or 3/4
	Grade 2 (mild to moderate new symptoms)	Delay nivolumab  Pulmonary and ID consults	Re-image every 1-3 days  If improves:

		
Monitor symptoms daily, possible hospitalization
 
1.0 mg/kg/day methylprednisolone or oral equivalent
 
Consider bronchoscopy, lung biopsy
	
When symptoms improve to near baseline, taper steroids over at least 1 month, and then resume nivolumab as per protocol. Consider prophylactic antibiotics
 
If not improved after 2 weeks or worsening: Treat as grade 3/4

	Grade 3/4 (severe new symptoms, new/worsening hypoxia; life threatening)	
Discontinue nivolumab
 
Hospitalize
 
Pulmonary and ID consults
 
2-4 mg/kg/day methylprednisolone or IV equivalent
 
Add prophylactic antibiotics for opportunistic infections
 
Consider bronchoscopy, lung biopsy
	
If improves to baseline: Taper steroids over at least 6 weeks
 
If not improving after 48 hours or worsening: Add additional immunosuppression

Hepatic / Liver Function Test Elevation	Grade 1 (AST or ALT > ULN to 3x ULN and/or total bili > ULN to 1.5x ULN)	Continue nivolumab as per protocol	
Continue LFT monitoring as per protocol
 
If worsens, treat as grade 2 or 3/4

	Grade 2 (AST or ALT >3.0 to $\leq$ 5x ULN and/or total bili > 1.5 to $\leq$ 3x ULN)	
Delay nivolumab
 
Increase monitoring LFTs to every 3 days
	
If returns to baseline: Resume routine monitoring and resume nivolumab
 
If elevation persist > 5-7 days or worsens: 0.5 – 1 mg/kg/day methylprednisolone or oral equivalent and when LFT returns to grade 1 or baseline, taper steroids over at least 1 month, consider prophylactic antibiotics, and resume nivolumab as per protocol

	Grade 3/4 (AST or ALT > 5x ULN or total bili > 3x ULN)	
Discontinue nivolumab
 
NOTE: May be delayed rather than discontinued if AST/ALT <math>\leq</math> 8xULN or total bili <math>\leq</math> 5x ULN
 
Increase LFT monitoring to every 1-2 days
 
1.0 to 2.0 mg/kg/day methylprednisolone or IV equivalent
 
NOTE: 2 mg/kg/day recommended for grade 4
 
Add prophylactic antibiotics for opportunistic infections
 
Consult gastroenterologist
	
If returns to grade 2: Taper steroids over at least 1 month
 
If does not improve in >3-5 days, worsens, or rebounds: Add mycophenolate mofetil 1 g bid If no response within an additional 3-5 days, consider other immunosuppressants

Endocrinopathies	Asymptomatic TSH elevation	Continue nivolumab as per protocol	If TSH < 0.5 x LLN or > 2x ULN, or consistently out of range in 2 measurements, include free T4 at subsequent cycles and treat as clinically indicated. Consider endocrinology consult
	Symptomatic endocrinopathy	
Evaluate endocrine function Consider pituitary scan (MRI)
 
Grade 3 drug-related endocrinopathies, adequately controlled with only physiologic hormone replacement do not require discontinuation. Adrenal insufficiency requires discontinuation regardless of control with hormone replacement.
 
Grade 4 drug-related endocrinopathy AEs, such as, hyper- or hypothyroidism, or glucose intolerance, that resolve or are adequately controlled with physiologic hormone replacement (corticosteroids, thyroid hormones) or glucose-controlling agents, respectively, may not require discontinuation.
 
Grade 4 drug-related adrenal insufficiency or hypophysitis requires discontinuation regardless of control with hormone replacement.
	
	Suspicion of adrenal crisis (e.g. severe dehydration, hypotension, shock out of proportion to current illness)	
Discontinue nivolumab for any drug-related grade 3 or 4 adrenal insufficiency
 
Rule out sepsis
 
Stress dose of IV steroids with mineralocorticoid activity
 
IV fluids
 
Consult endocrinologist
	
Dermatologic (Skin rash)	Grade 1-2 (covering $\leq$ 30% BSA)	
Continue nivolumab
 
Symptomatic therapy (e.g. antihistamines, topical steroids)
	
If persists >1-2 weeks or recurs:
 
Consider skin biopsy
 
Delay nivolumab
 
Consider 0.5-1.0 mg/kg/day methylprednisolone or oral equivalent.
 
Once improving, taper steroids over at least 1 month, consider prophylactic antibiotics, and resume nivolumab as per protocol

	Grade 3-4 (covering $>$ 30% BSA or with life)	
Delay or discontinue nivolumab
 
Consider skin biopsy
 
Consult dermatology
	
If improves to grade 1:
 
Taper steroids over at least 1 month and add prophylactic antibiotics

	threatening consequences)	1.0-2.0 mg/kg/day methylprednisolone or IV equivalent	Resume nivolumab as per protocol  NOTE: If SJS/TEN is diagnosed, permanently discontinue nivolumab
Neurologic	Grade 1 (asymptomatic or mild symptoms, intervention not indicated)	Continue nivolumab as per protocol	Continue monitoring.  If worsens, treat as grade 2 or 3/4
	Grade 2 (moderate symptoms, limiting instrumental ADL)	Delay nivolumab as per protocol Treat symptoms as clinically indicated Consider 0.5 to 1.0 mg/kg/day methylprednisolone or oral equivalent	If improves to baseline: Resume nivolumab as per protocol  If worsens: Treat as grade 3/4
	Grade 3/4 (severe symptoms; limiting self-care ADL; life threatening)	Discontinue nivolumab Neurology consult Treat symptoms as clinically indicated 1.0 – 2.0 mg/kg/day methylprednisolone or IV equivalent Add prophylactic antibiotics	If improves to grade 2: Taper steroids over at least 1 month  If worsens or atypical presentation: Consider IVIG or other immunosuppressive therapies as clinically indicated
All other immune-related AEs	Grade 3, or intolerable/persistent Grade 2	Delay nivolumab as per protocol Consider corticosteroid therapy	Ensure adequate evaluation to confirm etiology or exclude other causes; Resume nivolumab as per protocol if symptoms resolve
	Grade 4 or recurrent Grade 3	Discontinue nivolumab 1.0 to 2.0 mg/kg/day methylprednisolone or IV equivalent Add prophylactic antibiotics	Taper steroids over at least 1 month after improvement in symptoms

Any infusional drug, including nivolumab, may cause severe or life threatening infusion-reactions including severe hypersensitivity or anaphylaxis. Signs and symptoms usually develop during or shortly after drug infusion and generally resolve completely within 24 hours of completion of infusion. Dose modification and toxicity management guidelines for infusion reactions are provided in the Table below:

NCI CTCAE Grade	Treatment	Premedication at Subsequent Dosing
Grade 1 Mild reaction; infusion interruption not indicated; intervention not indicated	Increase monitoring of vital signs as medically indicated until the participant is deemed medically stable in the opinion of the investigator.	None
Grade 2 Requires therapy or infusion interruption but responds promptly to symptomatic treatment (e.g., antihistamines, NSAIDs, narcotics, IV fluids); prophylactic medications indicated for $\leq 24$ hrs	
Stop Infusion.
 
Additional appropriate medical therapy may include but is not limited to:
 
IV fluids Antihistamines NSAIDs Acetaminophen Narcotics
 
Increase monitoring of vital signs as medically indicated until the participant is deemed medically stable in the opinion of the investigator.
 
If symptoms resolve within 1 hour of stopping drug infusion, the infusion may be restarted at 50% of the original infusion rate (e.g. from 100 mL/hr to 50 mL/hr). Otherwise dosing will be held until symptoms resolve and the participant should be premedicated for the next scheduled dose.
 
Participants who develop Grade 2 toxicity despite adequate premedication should be permanently discontinued from further nivolumab treatment
	Participant may be premedicated 1.5h ( $\pm 30$ minutes) prior to infusion of nivolumab with: Diphenhydramine 50 mg po (or equivalent dose of antihistamine). Acetaminophen 500-1000 mg po (or equivalent dose of analgesic).
Grades 3 or 4 Grade 3: Prolonged (i.e., not rapidly responsive to symptomatic medication and/or brief interruption of infusion); recurrence of symptoms following initial improvement; hospitalization indicated for other clinical sequelae (e.g., renal impairment, pulmonary infiltrates) Grade 4: Life-threatening; pressor or ventilatory support indicated	
Stop Infusion.
 
Additional appropriate medical therapy may include but is not limited to:
 
Epinephrine** IV fluids Antihistamines NSAIDs Acetaminophen Narcotics Oxygen Pressors Corticosteroids
 
Increase monitoring of vital signs as medically indicated until the participant is deemed medically stable in the opinion of the investigator.
 
Hospitalization may be indicated.
 
**In cases of anaphylaxis, epinephrine should be used immediately.
 
Participant is permanently discontinued from further nivolumab treatment.
	No subsequent dosing

Appropriate resuscitation equipment should be available at the bedside and a physician readily available during the period of drug administration.

For further information, please refer to the Common Terminology Criteria for Adverse Events v4.0 (CTCAE) at <http://ctep.cancer.gov>

Nivolumab may be interrupted for situations other than treatment-related AEs such as medical / surgical events or logistical reasons not related to study therapy. Participants should be placed back on study therapy within 3 weeks of the scheduled interruption, unless otherwise discussed with the Sponsor. The reason for interruption should be documented in the patient's study record.

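### Minor safety wording: in the Grade 3/4 hepatic row, the 'or' in the delay note lets the normal liver value excuse the raised one, so in an isolated elevation neither cap ever forces nivolumab to stop

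*Combined protocol and SAP*

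**What the plan says.** The rule is in the combined protocol and SAP, Section 7, in the table of dose modifications for immune-related events, hepatic row, Grade 3/4.

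- Entry to the row: "AST or ALT > 5x ULN or total bili > 3x ULN". Either analyte is enough.
- Default action: "Discontinue nivolumab".
- Exception: a note saying "May be delayed rather than discontinued if AST/ALT" is at or below 8x ULN, or total bilirubin is at or below 5x ULN. The two limits are joined in the words "8xULN or total bili". Nothing ties a limit to the analyte that is raised.

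The text of Section 7 before the table adds three things. After a first Grade 3 event, nivolumab is held until the event falls to Grade 1 or below. After a second Grade 3 event or any Grade 4 event at least possibly due to nivolumab and not attributed to the vaccine, nivolumab in general ends. The reader is sent to the table for the specific indications to delay or discontinue.

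**The concern.** An exception with two numerical caps should withdraw permission to delay once the relevant cap is passed. As worded, this one does not. The row can be entered on one liver value alone, and the exception can be met on the other value alone. A patient with a marked isolated transaminase rise meets the exception through a normal bilirubin, and a patient with a marked isolated bilirubin rise meets it through normal transaminases.

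What is at stake is patient safety: possible re-exposure to nivolumab after a liver event that the stated caps seem meant to treat as disqualifying. The trial runs at several institutions, so a dosing rule that can be read in two ways may also be applied differently between sites.

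**Working it through.** No figure in the plan needs to be reproduced. The check is one of logic, using the four limits in the row. Let A be AST/ALT (the higher of the two) and B total bilirubin, both in multiples of ULN.

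- Row entered: A > 5 or B > 3.
- Delay permitted, literal wording: A ≤ 8 or B ≤ 5.
- Delay permitted, each cap applied to its own raised analyte: if A > 5 then A ≤ 8, and if B > 3 then B ≤ 5.

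**Isolated AST/ALT rise.** A > 5 and B ≤ 3. Since 3 < 5, B ≤ 5 always holds, so the literal note is met whatever the value of A. The 8x cap has no effect.

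**Isolated bilirubin rise.** B > 3 and A ≤ 5. Since 5 < 8, A ≤ 8 always holds, so the literal note is met whatever the value of B. The 5x cap has no effect.

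**When the literal note fails.** Only when A > 8 and B > 5 together.

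**What replaces it.** An analyte that is not raised is already under its cap (A ≤ 5 implies A ≤ 8; B ≤ 3 implies B ≤ 5). Within the row, the own-analyte reading is therefore identical to A ≤ 8 and B ≤ 5. Changing the connector to 'and' reproduces that reading exactly.

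Worked cases, where *discontinue* means that the exception is unavailable and the default stands:

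| A (x ULN) | B (x ULN) | Literal 'or' | 'And' (same as own-analyte) |
|---|---|---|---|
| 6 | 1 | delay allowed | delay allowed |
| 9 | 1 | delay allowed | discontinue |
| 15 | 1 | delay allowed | discontinue |
| 1 | 4 | delay allowed | delay allowed |
| 1 | 6 | delay allowed | discontinue |
| 6 | 4 | delay allowed | delay allowed |
| 9 | 4 | delay allowed | discontinue |
| 6 | 6 | delay allowed | discontinue |
| 9 | 6 | discontinue | discontinue |

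The readings part exactly when one cap is exceeded and the other is not. That covers isolated elevations above the cap, and also combined elevations with one value above its cap (9 and 4, or 6 and 6). The cases show the logic. They say nothing about how often each pattern would occur.

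**Effect of the Section 7 text.** The general rule removes most of what the note would otherwise let through, because any Grade 4 event and any second Grade 3 event should end nivolumab. A first Grade 3 event with one cap exceeded is left. The general rule does not fully settle the rest either, since it is qualified as general, it defers to the table for specifics, and this row covers Grades 3 and 4 together.

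**The case against.** The strongest answer is that nobody would read the note this way. It repeats the two analytes of the trigger in the same order with higher limits, so the natural reading pairs each cap with its own analyte. The literal reading makes both caps pointless in every isolated elevation, which is itself a reason to reject it. That is probably what was meant, and many clinicians would apply it so. But the trigger in the same row uses 'or' in its inclusive sense, and the note does not say that its own 'or' works differently.

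The second answer is that other safeguards narrow the gap. The default is to stop, the note only permits delay, and the drug is held until Grade 1 or below. Liver tests every one to two days, steroids and a gastroenterology consult apply under either reading. Holding and then resuming after a first Grade 3 event is also accepted policy in Section 7, on the ground that patients may still benefit. All of this stands, and it is why the point is minor. It does not make the caps bind.

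A reader might go further and infer that the plan allows nivolumab to resume after any severe hepatitis, including Grade 4. The documents do not support that: nothing requires re-dosing, and the Section 7 rule in general ends nivolumab after a Grade 4 event. A reader might also infer that the safety endpoint or the toxicity stopping boundary is compromised. It is not, because the event has the same grade, and so the same place in the Grade 3 or higher count, whether nivolumab is delayed or stopped.

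**Conclusion.** The point holds as a minor correction of safety wording. Read literally, the caps of 8x ULN for AST/ALT and 5x ULN for bilirubin never force discontinuation in an isolated elevation. They bind only when both are exceeded together.

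The practical gap is mainly a first Grade 3 hepatic event with exactly one cap exceeded. It leads to re-exposure only if the investigator applies the literal wording, chooses delay over the default, and the event resolves. This assumes that the general Section 7 rule is applied to this row as to others.

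The risk cannot be put in numbers. The documents state no hepatic event rate, and the row gives no numerical line between Grade 3 and Grade 4. No endpoint, sample size, stopping boundary or analysis changes.

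**What to change.** In the hepatic Grade 3/4 row, reword the note so that nivolumab may be delayed instead of discontinued only if AST/ALT is at most 8x ULN **and** total bilirubin is at most 5x ULN. The sponsor's clinical lead should confirm that this is the intended rule. No other text in Section 7 needs to change for this point.

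The cost is one table line in the next amendment. Delay stays available whenever both values are within their caps. The downside is slightly less discretion to rechallenge a patient above one cap, set against the Section 7 rationale that such patients might still benefit from treatment.

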## **8. Plan of Treatment**

The following section describes the schedule for prescreening, treatment, and clinical and laboratory evaluations. When a chemistry panel is indicated the following tests are performed: Chem 7 (including sodium, potassium, bicarbonate, BUN, creatinine, and glucose), ALT, AST, total bilirubin, alkaline phosphatase, amylase, thyroid stimulating hormone (TSH) and LDH. Whenever a CBC is indicated, this will include differential and platelet count. This plan is summarized in the Schema.

### **A. Prescreen (performed within 4 weeks of study registration unless otherwise noted)**

1. Confirm potential eligibility by history, pathology, diagnosis, and serial serum PSA levels; no exclusions by history
2. CT scan of abdomen and pelvis, bone scan
3. Sign consent form (to be done within 4 months prior to study registration)

### **B. Screening Evaluation (performed within 2 weeks of study Day 1; can coincide with prescreen evaluation)**

1. Physical examination, including vital signs, symptoms assessment, and ECOG performance score
2. Evaluation of blood cell counts (CBC with platelets), chemistry panel, serum prostate specific antigen (PSA), serum PAP, serum testosterone.
3. 20 ml peripheral blood (red-top tubes) for sera to evaluate baseline antibody responses, and 200 ml peripheral blood (green-top heparinized tubes) for T-cell response evaluation.
4. NaF PET/CT (scan within +/- 7 days of study visit, exceptions may be allowed with prior approval from the study PI.). NOTE: This PET scan is for research purposes only, will not be used to determine eligibility, and will not be used for clinical response evaluation or treatment decisions. NaF PET/CT should NOT be obtained within 2 days of GM-CSF injection.

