## Study Scheme:

Study Calendar:

Vaccine / Treatment Visit:	Pre-Screen (within 4 wks registration)	Screen/Randomization (within 2 weeks of day 1)	Day 1 (wk 0) – V1	Week 2 – V2 (+/- 3 d) d	Week 4 – V3 (+/- 3 d)	Week 6 - V4 (+/- 3 d)	Week 8 – V5 (+/- 3 d)	Week 10 - V6 (+/- 3 d)	Week 12 – V7 (+/- 3 d)	Week 16 – V8 (+/- 3 d)	Week 20 – V9 (+/- 3 d)	Week 24 – V10 (+/- 3 d)	Week 28 – V11 (+/- 3 d)	Week 32 – V12 (+/- 3 d)	Week 36 – V13 (+/- 3 d)	Week 40 – V14 (+/- 3 d)	Week 44 – V15 (+/- 3d)	Week 48 – V16 EOT (+/- 3d)	Week 60 – V17 (+/- 14d) k	Week 72 – V18 (+/- 14d) k	Week 84 – V19 (+/- 14d) k	Week 96 – EOS (+/- 14d) k	28-day Follow Up (+/- 7d) hp	Annual Long-Term F/U
	History & Physical Exam																							
Consenting	X																							
History	X																							
Physical Exam m		X n	X	X	X	X	X	X	X	X	X	X	X	X	X	X	X	X	X	X	X	X		
Toxicity assessment a		X	X	X	X	X	X	X	X	X	X	X	X	X	X	X	X	X	X	X	X	X		
Lab Tests																								
CBC b		X	X g		X	X		X	X	X	X	X	X	X	X	X	X	X	X	X	X	X		
Chemistry panel c		X	X g		X	X		X	X	X	X	X	X	X	X	X	X	X	X	X	X	X		
Serum testosterone		X																						
PSA l and PAP		X	X g		X o	X		X	X	X	X	X	X	X	X	X	X	X	X	X	X	X		
Procedures / Treatments																								
CT abdomen/pelvis f	X													X e					X e	X e	X e			
Bone scan	X													X e					X e	X e	X e			
NaF-PET/CT		X q,r						X q,r			X q,r													
Nivolumab			X	X	X	X	X	X	X	X	X	X	X	X	X	X	X	X	X	X	X			
PTVG-HP immunization			X	X	X	X	X	X	X	X	X	X	X	X	X	X	X	X	X	X	X			
rhGM-CSF adjuvant j				X	X	X	X	X	X	X	X	X	X	X	X	X	X	X	X	X	X			
Blood for immune studies		X			X			X			X			X			X			X			X i	

a Study coordinator or research nurse review of systems

b CBC to include differential and platelets

c Chemistry panel includes Chem7 (sodium, potassium, bicarbonate, BUN, creatinine, glucose), ALT, AST, total bilirubin, alkaline phosphatase, amylase, TSH (thyroid stimulating hormone), and LDH

d Time interval (+/- 3 days) is from last visit

e Can be +/- 7 days of this visit

f CT of chest only as clinically indicated

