g If not performed within 7 days of this visit

h 28 days +/- 7d after off-study date, if prior to week 48, otherwise this visit not required

i If not already collected within previous 60 days

j Only use GM-CSF adjuvant if serum PSA at week 4 (V3) is higher than that obtained at day 1 (V1).

k Can be +/- 14 days of this visit

l PSA values used for screening/eligibility should all be from same clinical laboratory; for day 1 and subsequent visits, all PSA values should be from same lab, but not necessarily from same lab as used for screening

m Physical exam to include vital signs and ECOG status

n Physical exam does not need to be repeated on Day 1 if obtained within 14 days prior to the visit

o PSA obtained at week 4 and used to determine whether GMCSF will be added can be obtained within 7 days of the visit

p Patients will be followed for adverse events for 90 days after the last dose of nivolumab

q NaF PET/CT within +/- 7 days of study visit, exceptions may be allowed with prior approval from the study PI. The same PET/CT scanner should be used for each individual subject.

r NaF PET/CT should NOT be done within 2 days of GM-CSF injection.

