## **6. Experimental Design**

This will be a single-arm, multiple-institution, two-stage phase II trial designed to evaluate the safety and effect of serial intradermal vaccinations of a DNA vaccine encoding PAP with or without rhGM-CSF, and co-administered with nivolumab, on serum PSA in patients with PSA-recurrent, non-metastatic, non-castrate prostate cancer. A total of 20-41 patients will be accrued, treated over a maximum of one year each, and followed for up to two years for evidence of radiographic progression. All subjects will be followed an additional 2 years after their last treatment for evidence of delayed adverse events. The treatment will be as follows:

Nivolumab 240 mg IV every two weeks x 6 beginning day 1, then every four weeks x 9 beginning week 12

pTVG-HP (100 µg) administered intradermally (i.d.) every two weeks x 6 beginning day 1, then every four weeks x 9 beginning week 12

rhGM-CSF (208 µg) administered intradermally (i.d.) every two weeks x 4 beginning week 4, then every four weeks x 9 beginning week 12 NOTE: Only administered to patients for whom serum PSA obtained week 4 > serum PSA obtained at day 1.

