### **C. First treatment visit (day 1)**

1. Physical examination, including vital signs, symptoms assessment, and ECOG performance score (not required if already obtained within 14 days)
2. Blood draw CBC, chemistry panel, PSA and PAP. May be done up to 7 days in advance of Day 1, and could coincide with screening evaluation.
3. pTVG-HP immunization intradermally on the deltoid area of the lateral arm (preferentially left arm) with 0.25 mL administered at each of two adjacent sites
4. Following vaccination, subjects will be observed for 60 min. for adverse events

5. Nivolumab 240 mg, administered intravenously over 30 minutes

D. Second treatment visit (week 2, 14 +/- 3 days after day 1 visit)

1. Symptoms assessment
2. pTVG-HP immunization intradermally on the deltoid area of the lateral arm (preferentially left arm) with 0.25 mL administered at each of two adjacent sites
3. Following vaccination, subjects will be observed for 60 min. for adverse events
4. Nivolumab 240 mg, administered intravenously over 30 minutes

E. Third treatment visit (week 4, 14 +/- 3 days after week 2 visit)

1. Physical examination, including vital signs, symptoms assessment, and ECOG performance score
2. Blood draw CBC, chemistry panel, PSA and PAP. NOTE: for this visit the PSA can be obtained up to 7 days prior to the visit in order to have the results available to determine whether rhGM-CSF will be co-administered.
3. 10 ml peripheral blood (red-top tube) for sera to evaluate baseline antibody responses, and 100 ml peripheral blood (green-top heparinized tubes) for T-cell response evaluation
4. pTVG-HP immunization intradermally on the deltoid area of the lateral arm (preferentially left arm) with 0.25 mL administered at each of two adjacent sites
5. NOTE: If serum PSA obtained at this visit is higher than that obtained at day 1 visit, then rhGM-CSF (208 µg) will be co-administered with the pTVG-HP immunization as adjuvant for this and all subsequent immunizations
6. Following vaccination, subjects will be observed for 60 min. for adverse events
7. Nivolumab 240 mg, administered intravenously over 30 minutes

F. Fourth treatment visit (week 6, 14 +/- 3 days after week 4 visit)

1. Symptoms assessment

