#### D. Quantitative Total Bone Imaging (QTBI) using NaF PET/CT

An assessment of small volume bone metastatic disease (potentially not detected by standard bone scintigraphy) and tumor growth rates will be conducted using QTBI. Patients selected to participate in the NaF PET/CT part of the study will be assessed at baseline, week 12, and week 24 by NaF PET/CT. Metastatic prostate cancer lesions in bone will first be localized and identified based on functional NaF PET uptake, assisted with the anatomical information

provided by CT scans. Segmentation will be performed using an automatic segmentation method (e.g. a fixed SUV threshold), and adjusted with physician guidance. Scans from different time points will be registered to one another using an articulated registration technique employing a rigid registration of skeletal elements (bones) from CT followed by registration optimization by combining with deformable registration of bones and lesions from NaF PET/CT. The lesions between pre-treatment and follow-up scans will be matched to establish longitudinal correspondence of the lesions. For each patient, comprehensive treatment response metrics will be calculated, consisting of SUVtotal (total disease burden), SUVmax (maximum intensity lesion), SUVmean (average intensity), the number of lesions, and total volume of bone lesions. In addition, imaging response metrics will be calculated for each individual lesion. This methodology will specifically be used to assess the growth rate of bone metastatic disease by evaluating changes from baseline to month 3 and from month 3 to month 6. In terms of logistics, each of the clinical centers has the capacity and expertise to perform NaF PET imaging.

NaF-PET/CT IMAGING PROCEDURES: To ensure uniformity as well as optimal data interpretation, a standardized image acquisition protocol will be utilized and the overall imaging analyses will be conducted centrally under the supervision of [name], PhD (co-investigator) at the University of Wisconsin Image Analysis Core (IMAC) facility, with all analysis blinded to study treatment arm. Please refer to the Standard Operating Procedures (SOP) document for NaF-PET/CT procedures, which will be adhered to at both sites, for details of image acquisition, image analysis, image interpretation, image submission for central review, and other imaging-related details.

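### The screening NaF PET/CT window lets an on-protocol baseline scan fall up to 6 days after the first nivolumab and pTVG-HP doses

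*Combined protocol and SAP*

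**What the plan says.** Section 8.B heads the screening evaluation "performed within 2 weeks of study Day 1; can coincide with prescreen evaluation", and the study calendar labels the same column "Screen/Randomization (within 2 weeks of day 1"). Neither sets a minimum gap between screening and day 1. Section 8.C shows that late screening is foreseen. It says of the day 1 bloods: "May be done up to 7 days in advance of Day 1, and could coincide with screening evaluation".

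For the screening scan, Section 8.B item 4 reads "NaF PET/CT (scan within +/- 7 days of study visit, exceptions may be allowed with prior approval from the study PI". Calendar footnote q, which is attached to all three NaF PET/CT entries, reads "NaF PET/CT within +/- 7 days of study visit, exceptions may be allowed with prior approval from the study PI". The window is two-sided and is the same as for the week 12 and week 24 scans.

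Section 6 starts both agents on day 1: "Nivolumab 240 mg IV every two weeks x 6 beginning day 1" and "pTVG-HP (100 µg) administered intradermally (i.d.) every two weeks x 6 beginning day 1".

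Section 9.D names the three scans as baseline, week 12 and week 24, describes the first as pre-treatment when lesions are matched over time, and measures growth by "evaluating changes from baseline to month 3 and from month 3 to month 6". Exploratory objective 5 relates lesions present at baseline to progression within one year. Section 10.D(4) gives the corresponding Cox and logistic regressions.

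**The concern.** A two-sided window suits an on-treatment scan. For a scan that has to come before treatment, the late side of the window must stop at the first dose, and here it does not. The scheduling rule in Section 8.B and footnote q permits something that the analysis description in Section 9.D excludes.

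At stake is the meaning of baseline in two exploratory analyses. Objective 5 needs a predictor measured before treatment. Objective 6 needs an untreated starting point for the first growth interval, because Section 2.F wants to learn whether treatment affects tumour growth rate.

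A scan done a few days after dosing would be on protocol, so it would not be flagged as a deviation, and no analysis rule removes it. A pre-treatment scan cannot be obtained afterwards. The imaging set is also small: Section 9.D limits it to selected patients, from a trial of at most 41.

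**Working it through.** The protocol gives no figure to reproduce here. The check lists the dates that the windows allow.

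**Inputs**
- Screening visit: 1 to 14 days before day 1 (Section 8.B heading and calendar column).
- Scan: from 7 days before to 7 days after the screening visit (Section 8.B item 4, footnote q).
- First dose of both agents: day 1 (Section 6; Section 8.C items 3 and 5).
- Second dose: 14 days after day 1, plus or minus 3 (Section 8.D).
- GM-CSF: first given at week 4 (Section 6). The 2-day gap between scan and GM-CSF therefore cannot limit the screening scan.

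**Latest permitted scan.** Count day 1 as 0. For screening k days before day 1, the last permitted scan day is 7 − k.

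| Screening, days before day 1 (k) | Last permitted scan day, relative to day 1 |
|---|---|
| 14 | −7 |
| 8 | −1 |
| 7 | 0 (day 1 itself) |
| 6 | +1 |
| 3 | +4 |
| 1 | +6 |

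The full permitted range runs from −14 − 7 = −21 to −1 + 7 = +6. A scan on a day after dosing is possible only for k = 1 to 6. If screening on day 1 itself counted as within two weeks, the upper limit would be +7.

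**How much of the window is affected.** There are 14 screening days × 15 scan days = 210 permitted combinations. Those after day 1 number 6 + 5 + 4 + 3 + 2 + 1 = 21. This counts what the text allows. It is not an expected frequency, because the documents do not say when sites will screen or scan.

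**Doses before the latest scan.** The earliest second dose is at 14 − 3 = +11, later than +6 or +7. Without a PI exception, at most one dose of each agent can precede the scan.

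**First growth interval.** Week 12 is nominally day 84. A scan at +6 leaves 84 − 6 = 78 days, a shortening of 6/84 = 7%. A scan at −21, which is properly pre-dose, gives 84 + 21 = 105 days. The permitted early scans thus move the interval more than the late ones do.

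**With a before-first-dose condition.** The permitted range becomes −21 to day 1 before dosing, and the post-dose combinations fall from 21 to 0.

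**The case against.** The strongest reply is that the protocol's intent is clear. The scan is listed under screening, the calendar places it ahead of the day 1 column, and Section 9.D calls it pre-treatment. On that reading, the 7 days are slack inside a screening period that ends at day 1, and most sites would scan before dosing anyway. Section 9.D also refers to a separate NaF PET/CT procedures document, not available here, which might address timing.

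This stands as evidence of intent, and nothing suggests that a post-dose baseline was wanted. It does not supply a limit. Where the protocol wants something done before treatment, it can say so: the eligibility bloods in Section 5.A item 8 are timed before first immunization, the day 1 bloods in Section 8.C may be drawn only in advance, and the first immune blood draw in Section 9.B precedes immunization. The scan has no such wording, and the PI exception is open-ended.

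Three stronger readings are tempting, and the documents do not support them:
- **All three imaging objectives depend on a pre-dose scan.** Objective 4 asks whether NaF PET/CT finds bone lesions that standard scintigraphy misses, and does not mention baseline. Only objective 5, directly, and objective 6, through the growth-rate definition, rely on it.
- **The growth comparison is materially distorted by the shorter interval.** Six days is minor beside the other permitted variation: up to 21 days before day 1, 7 days either side at week 12, and visits that may each move 3 days from the last (six steps, so up to 18 days by week 12). A growth rate can also use actual scan dates.
- **Early treatment effects contaminate the baseline.** No document shows that one dose of either agent changes NaF uptake within 6 days. The possibility is reason enough for a clear rule, but not for a claim of bias.

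**Conclusion.** The point holds as a mismatch between the scheduling rule and the use of the scan. As written, a baseline scan may be done up to 6 days after the first doses when screening falls 1 to 6 days before day 1, and later still with a PI exception.

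The consequence is small. It is confined to exploratory objectives 5 and 6. Section 8.B states that the screening scan plays no part in eligibility, clinical response evaluation or treatment decisions. The primary and secondary endpoints and the sample size are untouched. How many patients would be affected, and by how much, cannot be derived from the documents.

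The conclusion assumes that screening takes place before day 1 and that the unseen imaging procedures document does not already require a pre-dose scan. If it does, the protocol should still say the same. This is a cheap improvement, not a flaw that threatens the trial.

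**What to change.** For the screening scan only:
1. In Section 8.B item 4 and footnote q, add: 'and before the first dose of nivolumab or pTVG-HP'.
2. State in both places that a PI exception may not move this scan past the first dose.
3. In Sections 9.D and 10.D(4), state that a scan done after the first dose is not treated as baseline.

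Leave the rest of the pre-dose window as it is. A new 14-day lower limit is not needed and would exclude scans now allowed 15 to 21 days before day 1. Keep the 7-day windows at weeks 12 and 24.

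No extra scan is needed. The cost is a few lines of text and slightly tighter scan scheduling before day 1. A patient scanned late would lose the baseline value for these exploratory analyses.
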